## Description of quantitative data flow and entry system

The different forms of data will follow a different data flow and entry system as described below:

Detection data (gatekeeper logbook)

Figure 2 Data flow: Detection

Gatekeeper logbooks will be collected every two weeks by zone facilitator/psychosocial volunteers linked to that zone, and handed over to the clinical psychologists at TPO. The paper versions will be stored in a secure lockable cabinet at TPO's field office. A two-week timeframe is selected to allow for quality monitoring and follow up.

TPO's M&E Manager will enter the number of cases detected in a master excel sheet, stored on a password encrypted secure data server of the R&D Department of WCH.

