# **Outcome measures**

#### Primary outcome measure

The primary outcome is utilization of TPO's mental healthcare services among children and adolescents detected by the CCDT. Utilization in this study will be defined as initial encounters with TPO's mental healthcare among children and adolescents 6-18 years old or their caregivers, or re-entry into services for children and adolescents that have not been using TPO's services for 6 months. This is measured in two ways:

(1) Service utilization data: the number of children and or adolescents aged 6-18 years old that seek mental healthcare services from TPO, compared to utilization rates of practice-as-usual (i.e., during the pre-CCDT period). TPO's routinely collected monthly mental health service utilization data will be used for this. Following routine practices, upon intake, TPO's clinical team completes a 'case registration form' (see Annex 4.1).

- (2) The proportion of children and adolescents detected by the CCDT as in need of mental healthcare that seeks help at TPO. Two data sources will be used and compared for this:
  - a. Detection data: number of detected cases per gatekeeper. Gatekeepers will be trained in keeping a log of the number of detected children while using the CCDT (see Annex 4.2). Gatekeeper logbooks will be collected bi-weekly by one of WCH's facilitators attached to the zone and handed over the project officers who will be trained in entering the data in a digital master sheet.
  - b. Service utilization data: Number of cases contacting TPO as a result of a community gatekeeper trained in the CCDT handing out a referral card. The same 'monthly mental health service utilization data' (see outcome 1 above) will be used for this. TPO's clinical team will be trained to ask all new clients (children, adolescents or caregivers) an intake question regarding the reason for seeking help (including the community gatekeeper handing out the referral card as one of the options). This data is entered by the clinical psychologist in the 'case registration form' used upon entry.

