#### DATA COLLECTION AND PROCESSING

#### Description of data collected

Both quantitative and qualitative data will be collected.

Quantitative data

Quantitative data will be collected at two levels:

- 1) Detection data Gatekeepers will be provided with a logbook in which they will record the information about the detection (see Annex 4.2). A unique study ID will be created for each new case, this code will be linked to the gatekeepers' initials and cannot be traced back to the individual. The following information will be collected by gatekeepers:
  - o Study ID
  - Child's demographic information: age, gender, status (refugee/host), village, zone and settlement of residence
  - Contact details family
- Version of the CCDT used (i.e., the CCDT vignette that matched their observations)
- o Date of detection and engagement
- Date of verbal consent/assent obtained

This data will be collected in the zones where the CCDT is introduced, from the moment that the gatekeepers start using the CCDT, until the end of the project duration (i.e., April, 2023).

- 2) Service utilization (TPO) routine data will be collected at TPO for all clients seeking care. An anonymized client code will be assigned and used as the only identifier. The following variables will be collected in the Case Registration Form (see Annex 4.1):
  - Client ID
  - Demographic information: age, gender, status (refugee/host), village, zone and settlement of residence
  - Referral type: through CCDT or routine
    - This will be obtained through the referral card handed out by the gatekeeper using the CCDT (i.e., 'someone in the community approached me, handed out a referral card and encouraged me to seek help here')
  - Date of intake
  - Type of visit: new, re-entry or recurring/maintenance visit.
  - Mental health diagnosis
  - Service or type of treatment provided by TPO, or referral made

If treatment was initiated and completed.

This data will be collected from the beginning of the study in all zones, until the end of the project duration (i.e., April, 2023). A study specific data extraction sheet will be developed which will be used to collect all the information according to the primary and secondary outcomes.

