# Secondary outcomes:

- 1) Proportion of CCDT positives that sought help at TPO as a result of the CCDT (quantitative)
- 2) Acceptability and appropriateness of the CCDT (qualitative)
- 3) Feasibility of using the CCDT at scale (qualitative)
- 4) Attitudes towards mental health problems (qualitative)

Mixed-effects Poisson regression using a log link with clustering of zones within settlements and repeated measures within zones will be used to estimate the ratio of monthly mental health services utilization from the pre-CCDT to post-CCDT implementation periods. Utilization will be standardized using an offset of the log of the child population size estimate in each zone. CCDT implementation, time, and the interaction between CCDT and time since cross-over will be included as fixed effects. The effect of CCDT will be reported as an incidence rate ratio (IRR, 95% CI). Settlement and zone will be included as a random intercept. Heterogeneity across zones and settlements in time trends and treatment effects will be explored as random effects using the interaction between settlement/zone with time and CCDT implementation. If the assumptions of

Poisson regression are not fulfilled, we will estimate a mixed-effects negative binomial model. All analyses will be conducted using Stata, Version 17.

In addition, descriptive within-group analyses will be conducted to assess the proportion of children and adolescents detected by a gatekeeper using the CCDT that utilized TPO's mental healthcare during the entire project period. Among that group we will also assess the number of children and adolescents that initiated treatment and completed treatment.

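### No record linkage between logged detections and TPO intakes is specified, so the help-seeking proportion is, as written, a ratio of two separately gathered counts

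*Protocol*

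**What the plan says.** The help-seeking proportion answers research question 2. It is part (2) of the primary outcome measure and also the first secondary outcome in the Statistical Analysis plan.

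- **Denominator.** The Primary outcome measure section gives "Detection data: number of detected cases per gatekeeper", taken from the logbooks. The data-flow section says "TPO's M&E Manager will enter the number of cases detected in a master excel sheet".
- **Numerator.** This is the count of TPO contacts attributed to a gatekeeper's referral card. Referral type (CCDT or routine) is a field on the case registration form: "This will be obtained through the referral card handed out by the gatekeeper using the CCDT".
- **Identifiers.** Under Description of data collected, each detection receives a study ID, and "this code will be linked to the gatekeepers' initials and cannot be traced back to the individual". For TPO intakes, "An anonymized client code will be assigned and used as the only identifier". The intake variables listed there do not include the study ID.
- **Analysis.** The Statistical Analysis plan describes the share of detected children who used TPO care, and adds: "Among that group we will also assess the number of children and adolescents that initiated treatment and completed treatment".

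Other sections point elsewhere. The Primary outcome measure section gives data entry to "project officers who will be trained in entering the data in a digital master sheet", which is another role and possibly more than a count. The Informed Consent and Assent procedure has gatekeepers log names, contact details and age. The confidentiality sections, in the summary and in the main text, describe a master list of IDs and names held by TPO's M&E manager.

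**The concern.** A proportion of detected children who sought help needs each child in the numerator to be one of the children in the denominator. The Protocol describes two counts that are set against each other and no step that ties an intake to a detection. The only stated bridge is a category on the intake form, not an individual key.

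If the two counts are filled under different rules, their ratio is not the proportion that research question 2 asks for. The difference would not show in the reported figure. An identifier that was never captured at intake cannot be created at the analysis stage, so this has to be settled in the forms and the data flow.

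**Working it through.** The Protocol states no expected value, precision or sample size for this proportion, so there is no figure to reproduce. The check sets the rules for entering each count side by side and then illustrates the size.

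**1. Who enters each count** (Informed Consent and Assent procedure)

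| Situation | Detection count | CCDT intake count |
|---|---|---|
| Detected, no caregiver available; later attends TPO and consents there | Not counted (data not used, though help-seeking information is given) | Can be counted |
| Family refuses data release at detection; later attends and consents at TPO | Not counted | Can be counted |
| Logged at detection; attends TPO but refuses release there | Counted | Removed |
| Logged by two gatekeepers | Can be counted twice | Counted once |

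The first two rows push the ratio up and the last two push it down.

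**2. Are duplicates plausible?** Up to 200 gatekeepers cover 28 zones: 200 / 28 = 7.1 per zone on average. Each gatekeeper's catchment is the whole zone (Clusters section). Study IDs are tied to the gatekeeper's initials, so one child can hold two IDs. The consent section has gatekeepers note whether a detection is new or old. That flag is absent from the list under Description of data collected, and it would not survive entry of a bare count.

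**3. Size, by assumption.** Let

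R = p × c_u / [c_d × (1 + d)]

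- p: true share of detected children who go to TPO, taken as equal in logged and unlogged children
- c_u: share of those help-seekers who are counted as CCDT intakes
- c_d: share of detected children who are logged
- d: duplicate entries per logged child

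The anchor p = 0.67 is the figure that the Protocol's background gives for the adult tool in Nepal; 0.40 is an arbitrary lower value. The ranges for c_u and c_d (0.70 to 1.00) and d (0.10 to 0.20) are assumptions.

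- p = 0.67, d = 0: lowest 0.67 × 0.70 / 1.00 = 0.47; highest 0.67 × 1.00 / 0.70 = 0.96.
- p = 0.40, d = 0: lowest 0.40 × 0.70 / 1.00 = 0.28; highest 0.40 × 1.00 / 0.70 = 0.57.
- p = 0.67, c_u = c_d = 1: with d = 0.10, 0.67 / 1.10 = 0.61; with d = 0.20, 0.67 / 1.20 = 0.56.

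With no duplicates, R equals p only when c_u = c_d.

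**4. What matching would change.** Among distinct logged children the matched proportion is p × c_u, if c_u is the same for logged and unlogged children. In the upward case it gives 0.67 × 1.00 = 0.67 instead of 0.96. In the downward case it stays at 0.67 × 0.70 = 0.47. Matching therefore removes the errors from unlogged intakes and from duplicates, but not the loss from refusals at TPO.

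**The case against.** A reader might infer that detected children cannot be matched to intakes at all. The documents do not support that. Logbooks hold names, contact details and age. TPO needs family name, age and phone number to delete the records of families who refuse. The master list of IDs and names is held by the same role that keys the detections. Clinical psychologists check that referred children are captured and correctly coded. The Data management section plans distribution checks on logbooks, which a bare count would hardly allow. A matching route may exist, and the annexed forms, which are not shown, might carry a key. What remains is that no section says the list covers both study IDs and client codes or will be used for linkage, and that route conflicts with the statements that codes are untraceable and the only identifier.

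Several further objections stand:

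- Treatment initiation and completion can be tabulated for CCDT-coded intakes from TPO records alone.
- Age can be checked on the intake form and on the paper logbooks.
- The delay from detection to contact is not an outcome of this trial.
- The numerator is already limited to intakes attributed to a referral card, so the two totals are not unrelated.
- The ends of the illustrated ranges need one source at its worst while the other is complete.

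Linkage detail can often wait for a later plan, but this case differs in that the referral card and intake form must capture the key at the time.

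**Conclusion.** The point holds in this form: the Protocol specifies no linkage and, followed as written, yields a ratio of two separately gathered counts whose numerator need not lie within its denominator. The bias can go either way. Its size is unknown, because the Protocol gives no rates of refusal, absent caregivers or duplicate logging; the range 0.47 to 0.96 around 0.67 rests wholly on assumed capture shares.

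The stepped-wedge rate ratio uses TPO counts alone and is not affected. The help-seeking proportion is descriptive, but it is the whole answer to research question 2.

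Two contradictions need resolving in any case: who keys the logbooks and what they key (project officers entering the data, or the M&E Manager entering a number), and whether IDs can be traced to a child (Description of data collected, against the consent and confidentiality sections).

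**What to change.** 1. In the data-flow section, key one row per logged detection: study ID, date, age, gender, zone, CCDT version, new or old.
2. Write the study ID on the referral card and record it on the case registration form. Alternatively, state that the master list links study IDs to client codes. In either case, bring the identifier statements under Description of data collected into line.
3. Define the help-seeking proportion as logged, de-duplicated detections with a matched TPO intake, divided by all logged, de-duplicated detections.
4. Report unmatched CCDT-coded intakes and the simple ratio of counts alongside.
5. Name one data-entry role in both the Primary outcome measure section and the data-flow section.

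The cost is one extra form field and more keying from logbooks already collected every two weeks. Lost cards will lower the matched figure, which is why both figures should be shown. Refusal of data release at TPO still removes some help-seekers and should be stated as a limitation.

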## Service utilization (case registration forms)

Figure 3 Data flow: Service utilization

Following routine practices, all clinical data will be collected and consolidated by the clinical team at TPO. Case registrations forms will be completed by the clinical team using an electronic data entry form on a tablet. Data entered will be saved and stored on a password encrypted secure data server of the R&D Department of WCH, which will be password protected and synced. Access to the study data sets will only be accessible by the WCH core research team members.

Pretesting of data collection tools

Data collection tools will be pretested to ensure consistency prior to the study start:

- The Case Registration form: will first be used at TPO service points together with other
  case registration forms, prior to the study start to ensure adaptation to the local context
  during routine serve provisions,
- The gatekeeper log book: will be pretested during the training. Information that is not clear will be updated prior to the study start. This will be translated to Swahili, Kinyabwisha, Lugbara, Kakwa, Kuku, and Juba Arabic.
- Interview tools (FGD and Supervision Topic Guides, and Social Distance Scale): will be pretested prior to using the tools. A number of selected gatekeepers will be invited for a meeting after reading information sheet and signing consent form, during this meeting, selected questions in the topic guides and social distance scale will be asked. Questions which are not clear, will be changed. The tools will also be translated to Swahili, Kinyabwisha, Lugbara, Kakwa, Kuku, and Juba Arabic.

## **Data management**

The WCH Data Management Policy serves as guidance on all data management and data sharing issues (policy available upon request).

Quantitative data

To further improve the quality of data collected, the research coordinator/co-investigator will conduct routine data checks and follow up to check for any inconsistencies and missing data in the database. Any errors identified in the data collected will be sent to the field teams through the M&E managers for correction.

Statistical monitoring will also be implemented to look at variables for which distributions differ from the rest of the observed data, to highlight systematic (non-random) faults in filling the case registration forms and logbooks, compliance, SAEs, and to guide targeted monitoring. Comparison of distributions is made by statistical tests or models.

At the end of the data collection exercise, a final data review will be conducted by the coinvestigators and the M&E Managers, and the remaining data issues will be adjudicated.

The paper data files will be collected from the field offices on a monthly basis and stored in a locked cabinet in the WCH office.

#### Qualitative data

The project officer will upload the note forms on a password encrypted secure data server of the R&D Department of WCH after each supervision meeting.

Audio files will be stored on a password encrypted secure data server of the R&D Department of WCH after each supervision meeting. The server will be password protected and accessed from password protected and encrypted laptops. The project officer will only get the rights to upload documents, not to access any data. The paper data files will be collected from the field offices on a monthly basis and stored in a locked cabinet in the WCH office.

## Data security

Data entered electronically will be backed-up securely and password protected and encrypted. Any queries identified will be resolved promptly by the trial management team. Data entered on the server will only be available to the WCH CCDT research team, the M&E managers and project officers. The latter parties and any other external parties who require access to the data will only have access once a data sharing agreement has been signed, in which the party agrees to abide by the WCH Data Management Policy. Paper copies of informed consent forms (i.e., signed release of information forms) and data files will be collected from the field offices on a monthly basis and be stored securely in the lockable cabinet at one of TPO's field offices in the settlement.

Length of data retention, archiving conditions and management

Both qualitative and quantitative data will be stored for a period of at least 7 years after completion of the study. Any modification or deletion of data will be granted via the standard authentication and access-control features. Mental health records will be stored at TPO as per standard practices.

## Data ownership and sharing

WCH has, in all cases, ownership of the research data, and for the purpose of this study a data sharing agreement will be signed between WCH and TPO.

## Statistical Analysis plan

We will present the following results, based on both qualitative and quantitative data:

Primary outcome: Utilization of mental healthcare services (quantitative). This will be determined in three ways: (1) Trends in monthly utilization data from TPO's service points; (2) comparison of clusters where the CCDT has been implemented (experimental condition) with clusters where the CCDT has not yet been implemented (control condition); and; (3) proportion of CCDT cases detected that sought help at one of TPO's service points. This data will be captured through routine reporting using the referral card, and intake questions.

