# **Secondary objectives**

- 1. To examine the proportion of help-seeking (i.e., mental health care utilization) following pro-active case detection using the CCDT (independent of between-group comparisons).
- 2. To examine implementation outcomes in terms of the acceptability, appropriateness, and feasibility of using the CCDT at scale for community gatekeepers.
- 3. To examine community gatekeepers' attitudes towards mental health problems after the introduction of the CCDT, relative to rates pre-training.

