The impact of the above outcome measures will be determined in three ways: (1) Trends in monthly utilization data from TPO's service points; (2) comparison of clusters where the CCDT has been implemented (experimental condition) with clusters where the CCDT has not yet been implemented (control condition); and; (3) proportion of CCDT cases detected that sought help at one of TPO's service points. This data will be captured through routine reporting using the referral card, and intake questions.

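### Three unranked results determine the primary outcome, only one of them uses the randomisation, and the help-seeking proportion is labelled both primary and secondary

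*Protocol*

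**What the plan says.** The Statistical Analysis plan section names utilization of mental healthcare as the primary outcome and continues: "This will be determined in three ways: (1) Trends in monthly utilization data from TPO's service points". The second way is "2) comparison of clusters where the CCDT has been implemented (experimental condition) with clusters where the CCDT has not yet been implemented (control condition", and the third is "3) proportion of CCDT cases detected that sought help at one of TPO's service points". The end of the Primary outcome measure section gives the same list: "The impact of the above outcome measures will be determined in three ways: (1) Trends in monthly utilization data from TPO's service points". Neither place ranks the three or says which one settles the question.

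Earlier in the Primary outcome measure section the outcome has two measures, not three. Item (1) is the number of children and adolescents aged 6-18 who seek care at TPO, set against practice-as-usual. Item (2) is "The proportion of children and adolescents detected by the CCDT as in need of mental healthcare that seeks help at TPO".

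The same proportion is also given secondary status. The first of the Secondary objectives is "To examine the proportion of help-seeking (i.e., mental health care utilization) following pro-active case detection using the CCDT (independent of between-group comparisons", which also appears in the protocol summary. The Secondary outcomes list in the analysis section opens with "Proportion of CCDT positives that sought help at TPO as a result of the CCDT (quantitative".

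The mixed-effects Poisson model, whose CCDT effect is reported as an incidence rate ratio (IRR) with a 95% confidence interval, is described below that Secondary outcomes list. The proportion is assigned to a descriptive, within-group analysis over the whole project period.

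**The concern.** A trial of effectiveness needs one result, fixed in advance, that answers the primary question. Here three results share that role on paper, and they differ in what they can show. The zone comparison is protected by the randomised order of roll-out. A monthly trend is not: in a stepped wedge the share of exposed zones rises with calendar time, so an unadjusted rise in utilization mixes any CCDT effect with whatever else changed. The proportion exists only among detected children, so it has no control value, and the protocol sets no threshold for it.

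As the text stands, the authors could report a rising trend or a high help-seeking proportion as a primary result while the randomised IRR showed nothing, and they would not have departed from the protocol. The double labelling of the proportion adds to this, since either label can be cited afterwards.

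**Working it through.** No figure in the protocol is in dispute, so the check sets the sections side by side.

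**1. Status of the proportion of detected children who seek help**

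| Protocol section | Status given |
|---|---|
| Primary outcome measure, item (2) | primary |
| Primary outcome measure, closing list, way (3) | primary |
| Statistical Analysis plan, primary outcome, way (3) | primary |
| Study objectives (protocol summary) | secondary |
| Secondary objectives | secondary |
| Statistical Analysis plan, Secondary outcomes, item 1 | secondary |
| Secondary outcome measure (three items) | not listed |

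That is three primary labels, three secondary labels and one omission for one quantity.

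**2. Which ways use the randomisation**

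- *Trends:* no comparator is named. The roll-out moves four zones per monthly step, and 28 / 4 = 7 steps. Once the last group has crossed over, no zone remains in the control condition, yet utilization data are collected until April 2023.
- *Implemented versus not-yet-implemented zones:* this is the randomised contrast.
- *Proportion:* the objectives themselves describe it as independent of comparisons between groups, and its analysis is descriptive.

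So one of the three uses the randomisation.

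**3. What the rest of the protocol implies**

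- The primary objective concerns utilization under the CCDT against practice-as-usual.
- The Sample Size section powers a 20% difference in utilization between the pre-CCDT and post-CCDT periods, using a stepped-wedge design effect. It says nothing about sizing a trend or a proportion.
- The only inferential model estimates the ratio of monthly utilization between those periods.

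All three point to the second way, but no sentence calls it the primary analysis.

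**4. The population in the lead definition**

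The first sentence of the Primary outcome measure section limits the primary outcome to children detected with the CCDT. Before cross-over no gatekeeper in the zone has been trained in the tool, so no child there is detected by it. Read literally, the control count is zero by construction and a rate ratio against it is undefined. Item (1) of the same section and the first row of Table 1 instead count encounters among all children and adolescents aged 6-18, which is what the comparison needs.

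**5. Whether the model gives one number**

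The fixed effects are CCDT, time, and CCDT by time since cross-over. Write X for CCDT (0 or 1), s for time since cross-over, and b1 and b2 for the CCDT and interaction coefficients. At a given calendar time and zone the log rate under CCDT exceeds that under control by b1 + b2 × s, so

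IRR(s) = exp(b1 + b2 × s).

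Unless b2 = 0, the IRR changes with s. With s counted from zero, exp(b1) is only the effect at cross-over. Naming the model is therefore not enough; the contrast must be named too.

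**The case against.** The strongest reply is that a careful reader can already find the main analysis. The objective, the first research question, the power statement and the only regression model all concern utilization with and without the CCDT, and the effect is to be reported as an IRR. The proportion is openly descriptive. The model contains time as a fixed effect, so the IRR itself is adjusted for secular change. Monthly trends may be meant only as description, and a separate statistical analysis plan, not available here, may name the primary analysis.

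Most of this stands, and it limits the point. A reader might infer that no result decides the trial, or that the randomised analysis is missing. The documents do not support that: the analysis is there and is the evident centre of the design. A reader might also treat the three ways as three chances of success and calculate an inflated false-positive rate. The documents do not support that either. They state no test, significance level or success rule for the trend or the proportion, and the ways draw on overlapping utilization data.

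The reply does not remove the contradiction. The protocol says in two places that the primary outcome is determined by all three ways, and it gives the proportion opposite labels. A later document could fill a gap, but it could not make these statements agree. If trends are meant as description, they do not belong among the ways of determining the primary outcome.

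**Conclusion.** The point holds as an undeclared and contradictory hierarchy. Three unranked ways determine the primary outcome and one uses the randomisation. The help-seeking proportion is primary in three places, secondary in three, and absent from one secondary list. The lead definition names a population that control months cannot contain. The risk is selective emphasis: an uncontrolled trend or a within-group proportion presented as a primary result beside a null IRR.

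The conclusion rests on the protocol's wording alone. It assumes no particular alpha, variance or size of secular trend, so it carries no numerical error rate. It does not imply that the randomised comparison is absent or wrongly chosen. The change is worth making because it removes a route to a biased claim and only states what the design already implies.

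**What to change.** Name one primary result: the utilization rate ratio, CCDT versus pre-CCDT, for all initial encounters or re-entries at TPO aged 6-18 over the randomised roll-out months, from the mixed-effects count model already described. Because of the interaction with time since cross-over, state which single IRR contrast is primary.

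Then align the text:

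- **Statistical Analysis plan, and the closing list of Primary outcome measure:** take ways (1) and (3) out of the primary outcome, and describe monthly trends as descriptive.
- **Primary outcome measure, two-item list:** keep item (1), which is the utilization measure, and move item (2) to secondary. The numbering differs from the three-way list, so the same deletion cannot be applied to both.
- **Primary outcome measure, lead sentence:** remove the restriction to CCDT-detected children.
- **Secondary outcome measure:** add the proportion.
- **Secondary outcomes in the analysis section:** keep the proportion there, and move the model description under the primary outcome.

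The cost is wording in these sections and one decision on the contrast. No new data are needed and the number of zones does not change, since the Sample Size section already addresses the utilization comparison.
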